#### **8.4.5.2. Exposure During Breastfeeding**

An EDB occurs if:

- A female participant is found to be breastfeeding while receiving or after discontinuing study intervention.
- A female nonparticipant is found to be breastfeeding while being exposed or having been exposed to study intervention (ie, environmental exposure). An example of environmental EDB is a female family member or healthcare provider who reports that she is breastfeeding after having been exposed to the study intervention by skin contact.

The investigator must report EDB to Pfizer Safety within 24 hours of the investigator's awareness, irrespective of whether an SAE has occurred. The information must be reported using the CT SAE Report Form. When EDB occurs in the setting of environmental exposure, the exposure information does not pertain to the participant enrolled in the study, so the information is not recorded on a CRF. However, a copy of the completed CT SAE Report Form is maintained in the investigator site file.

An EDB report is not created when a Pfizer drug specifically approved for use in breastfeeding women (eg, vitamins) is administered in accordance with authorized use. However, if the infant experiences an SAE associated with such a drug, the SAE is reported together with the EDB.

#### **8.4.5.3. Occupational Exposure**

The investigator must report any instance of occupational exposure to Pfizer Safety within 24 hours of the investigator's awareness using the CT SAE Report Form, regardless of whether there is an associated SAE. Since the information about the occupational exposure does not pertain to a participant enrolled in the study, the information is not recorded on a CRF; however, a copy of the completed CT SAE Report Form must be maintained in the investigator site file.

#### **8.4.6. Cardiovascular and Death Events**

Not applicable.

#### **8.4.7. Disease Related Events and/or Disease Related Outcomes Not Qualifying as SAEs**

The following disease related events (DREs) are common in participants with ALL independent of exposure to study intervention, can be serious/life threatening:

- Febrile neutropenia;
- Neutropenic sepsis;
- Disease progression.
- The following occurring post HSCT and after discontinuation of inotuzumab ozogamicin:
  - Acute GvHD;
  - Infection requiring IV antibiotics;
  - Hemorrhage/bleeding;
  - Weight loss/anorexia;
  - Acute kidney injury;

- Nausea/vomiting/diarrhea;
- Thrombocytopenia/anemia.

Because these events are typically associated with the disease under study, they will not be reported according to the standard process for expedited reporting of SAEs even though the event may meet the definition of an SAE, unless the Investigator believes that there is a causal relationship between the investigational product. These events will be recorded on the corresponding CRF page in the participant's CRF within the appropriate time frame.

NOTE: However, if either of the following conditions applies, then the event must be recorded and reported as an SAE (instead of a DRE):

- The event is, in the investigator's opinion, of greater intensity, frequency, or duration than expected for the individual participant.

OR

- The investigator considers that there is a reasonable possibility that the event was related to study intervention.
- Grade 5 (or with an outcome of fatal).

#### **8.4.8. Adverse Events of Special Interest**

AESI constitute AEs (serious or non-serious) of scientific and medical concern in the evaluation of inotuzumab ozogamicin, for which in addition to ongoing monitoring, rapid communication by the Investigator to the Sponsor is considered appropriate. Such events may require further investigation in order to characterize and understand them. AESI may be added or removed during a study by Protocol Amendment.

#### **Reporting of AESI With Immediate Notification**

Investigator should notify the sponsor immediately (ie, within 24 hours) of the following events, as per SAE notification and/or using the pregnancy form (whichever is applicable):

- Hy's Law cases (see [Section 10.5](#))
- Potential VOD/SOS Cases (see [Section 8.4.8.2](#))
  - All suspected cases of hepatic SOS, irrespective of timing, causality and severity, should be reported in the AE CRF. If the event is deemed serious by the investigator, the SAE reports should include a complete list of all anticancer therapy administered before, during and after study therapy, including pre- and post-study HSCT conditioning, GVHD prophylaxis and treatment, and all concomitant medications used for prevention of hepatic toxicity (eg, ursodiol, defibrotide, low molecular weight heparin) and/or for the treatment of SOS (ie, defibrotide).

- Exposure during Pregnancy (see [Section 8.4.5.1](#))
- Second primary malignancy

Reporting of AESI Without Immediate Notification (unless assessed as SAE [see [Section 8.4.1.1](#) for reporting timeframe])

- Neurotoxicity
- Nephrotoxicity
- QT abnormalities (defined as Grade 3, 4, prolongation or QTcF post-baseline absolute value of >500 msec)
- Interstitial lung disease
- Pancreatitis
- Myelosuppression/cytopenia including Infections and Hemorrhages

AESIs are examined as part of routine safety data review procedures throughout the clinical trial and as part of signal detection processes. Should an aggregate analysis indicate that these prespecified events occur more frequently than expected, eg, based on epidemiological data, literature, or other data, then this will be submitted and reported in accordance with Pfizer's safety reporting requirements. Aggregate analyses of safety data will be performed on a regular basis per internal SOPs.

All AESIs must be reported as an AE or SAE following the procedures described in [Sections 8.4.1](#) through [8.4.4](#). An AESI is to be recorded as an AE or SAE on the CRF. In addition, an AESI that is also an SAE must be reported using the CT SAE Report Form.

#### **8.4.8.1. Lack of Efficacy**

The investigator must report signs, symptoms, and/or clinical sequelae resulting from lack of efficacy. Lack of efficacy or failure of expected pharmacological action is reportable to Pfizer Safety only if associated with an SAE.

#### **8.4.8.2. Potential VOD/SOS Cases**

All cases of VOD, also known as SOS, regardless of causality, severity and treatment arm must also be reported as an SAE for the entire duration of study participation up to 2 years after the first dose of inotuzumab ozogamicin, including the Follow-up period ([Table 1](#)). Events of VOD which occur thereafter should be reported following the SAE reporting criteria. In the event of serious or severe hepatic adverse events, patients should have a hepatology consultation and workup including (but not limited to), weights, infectious hepatitis testing (A, B, C). When evaluating liver toxicity, inform the radiologist of the potential for hepatic vascular disease. When VOD is in the differential diagnosis, a right upper quadrant ultrasound with color flow doppler (including resistive indices to hepatic

artery flow and evaluation of hepatic venous outflow) should be performed. In addition, the radiology report should describe common bile duct, the degree of gall bladder wall thickening in millimeters, and the volume of ascites should be estimated as closely as possible (ie, small and localized, moderate and generalized, or large and generalized). Assessment of abdominal tumor(s); collection of alcohol use information (historical, current); prior hepatitis or a related condition (either infectious or noninfectious, including nonalcoholic steatohepatitis [NASH, also known as nonalcoholic fatty liver or NAFL] and alcoholic steatohepatitis [ASH]), laboratory tests (including, but not limited to, conventional liver function tests, INR/ prothrombin time (PT), albumin, and ammonia levels), and information from liver biopsy or autopsy if performed.

Results of all assessments, signs and symptoms should be recorded in the CRF (including imaging results, biopsy results, vital signs [including changes in weight], detailed pertinent physical exam, laboratory values, nonstudy medications [including herbal supplements and herbal teas, if applicable], sites of disease other adverse events particularly recent and/or concurrent infections, and other nonstudy treatments); unplanned CRF pages can be used if necessary. Assessment (recording) of weights in a patient experiencing any hepatic event is important because it can help in the differential diagnosis, given the association of fluid retention with portal hypertension and VOD. One of the major distinctions between most acute liver disorders in oncology patients and VOD is the presence of portal hypertension, which leads to renal retention of salt and water, and thus, to abrupt gains in weight.

For this study, criteria for VOD (also known as SOS) are defined as:

- a. Classical VOD (first 21 days after HSCT):
  - Bilirubin  $\geq 2$  mg/dL and two (or more) of the following criteria must also be present;
    - Painful hepatomegaly;
    - Weight gain  $>5\%$ ;
    - Ascites.
- b. Late onset VOD (>21 days after HSCT):
  - Classical VOD beyond Day 21;
  - or
  - Histologically proven VOD;
  - or
  - Two or more of the following criteria must be present:

- Bilirubin >2 mg/dL;
- Painful hepatomegaly;
- Weight gain >5%;
- Ascites.

AND hemodynamical and/or ultrasound evidence of VOD.

For this study, severity of VOD is defined as follows (Table 9).

**Table 9. VOD Severity Grading (Patients Belong to the Category that Fulfills Two or More Criteria)a**

	Mild (Grade 1) b	Moderate (Grade 2) b	Severe (Grade 3)	Very severe (Grade 4) c
Time since first clinical symptoms d	>7 days	5-7 days	≤4 days	Any time
Bilirubin (mg/dL)	≥2 and <3	≥3 and <5	≥5 and <8	≥8
Bilirubin (umol/L)	≥34 and <51	≥51 and <85	≥85 and <136	≥136
Bilirubin kinetics			doubling ≤48 hr	
Transaminases	≤2 × ULN	>2 and ≤5 × ULN	>5 and ≤8 × ULN	>8 × ULN
Weight increase	<5%	≥5% and <10%	≥5% and <10%	>10%
Renal Function	<1.2 × baseline at HSCT	≥1.2 and <1.5 × baseline at HSCT	≥1.2 and <1.5 × baseline at HSCT	≥2 × baseline at HSCT or other signs of MOD/MOF

Abbreviations hr=hour; HSCT=hematopoietic stem cell transplant; MOD=multi-organ dysfunction; MOF=multi-organ failure; ULN=upper limit of normal.

- If patients fulfill two or more criteria in two different categories, they must be classified in the most severe category. Patients weight increase ≥5% and <10% is considered by default as a criterion for severe VOD; however, if patients do not fulfill other criteria for severe VOD, weight increase ≥5% and <10% is therefore considered as a criterion for moderate VOD.
- In the case of presence of two or more risk factors for VOD, patients should be in the upper grade.
- Patients with multi-organ dysfunction must be classified as very severe.
- Time from the date when the first signs/symptoms of VOD began to appear (retrospectively determined) and the date when the symptoms fulfilled VOD diagnostic criteria.

See also [Section 10.10 Appendix 10](#) for guidance about recommendation for patients proceeding to HSCT and potential VOD cases.

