6.6.1. Adverse Events

All analyses will be based on treatment emergent events unless otherwise specified. Treatment emergent is defined in [Section 3.5.1](#). AEs not considered treatment emergent will be flagged in data listings.

A high level summary of TEAEs (all causality), TEAEs (treatment related) and Cycle 1 TEAEs (treatment related) will include the number and percentage of participants with:

- Any TEAE;
- Serious TEAE;
- TEAE with CTCAE Grade 3-4;
- Grade 5 TEAE;

- TEAEs leading to dose reductions of inotuzumab ozogamicin;
- TEAEs leading to dose delay of inotuzumab ozogamicin;
- TEAEs leading to permanent discontinuation of inotuzumab ozogamicin.

Additionally, the number of events reported for each of the categories above will be provided. Each unique adverse event at the PT level for a participant is included in the count.

Seriousness, toxicity grade, action taken (interruption, reduction, and withdraw) are as reported by the investigator on the adverse event CRF.

Summaries of TEAE by SOC and PT in decreasing frequency will be provided for:

- TEAEs (All Causality);
- TEAEs by Maximum Toxicity Grade (All Causality);
- TEAEs (Treatment related);
- TEAEs by maximum toxicity grade (Treatment related);
- Serious TEAEs (All causality);
- Post-HSCT SAE (All causality);
- Serious TEAEs (Treatment related); and
- Post-HSCT SAE (Treatment related).

An event will be considered treatment related if the investigator considers so.

The following summaries will be provided by PT only (ie, summaries will not include SOC) in decreasing frequency:

- TEAEs (All causality);
- TEAEs (All causality) experienced by $\geq 10\%$ of participants;
- TEAEs (All causality) by maximum toxicity grade;
- Grade 3-5 TEAEs (All causality and Treatment related);
- TEAEs leading to dose delays of inotuzumab ozogamicin (all causality);
- TEAEs leading to dose reductions of inotuzumab ozogamicin (all causality);

- TEAEs leading to permanent discontinuation of inotuzumab ozogamicin (all causality);
- Serious TEAEs (all causality); and
- Post-HSCT SAEs (all causality).

Each participant will be counted only once within each SOC and PT.

As described in [Section 5.3](#), in case a participant has events with missing and/or non missing toxicity grades, the maximum of the non-missing grade will be displayed. Missing grade will only be displayed in the event that only one event has been reported for a participant and the grade is missing.

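### Table 9 puts one renal band in two VOD grades and leaves 1.5 to <2 × baseline in none, so a post-transplant VOD grade can fall as kidney function worsens

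*Protocol*

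**What the plan says.** Protocol section 8.4.8.2 introduces the grading table with "For this study, severity of VOD is defined as follows (Table 9". A patient belongs to the category in which two or more criteria are met.

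The renal row of Table 9 reads as follows, every ratio being relative to the value at HSCT:

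| Mild (1) | Moderate (2) | Severe (3) | Very severe (4) |
|---|---|---|---|
| <1.2 × | ≥1.2 and <1.5 × | ≥1.2 and <1.5 × | ≥2 ×, or other signs of multi-organ dysfunction or failure |

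The Moderate and Severe cells are both printed as "≥1.2 and <1.5 × baseline at HSCT". Four notes to the table bear on how it is applied:

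- Footnote a, conflicts: "If patients fulfill two or more criteria in two different categories, they must be classified in the most severe category".
- Footnote a, weight: a gain of 5 to <10%, which also appears in two columns, "is considered by default as a criterion for severe VOD". It reverts to a Moderate criterion when no other Severe criterion is met.
- Footnote b, marked on Grades 1 and 2: "In the case of presence of two or more risk factors for VOD, patients should be in the upper grade".
- Footnote c: "Patients with multi-organ dysfunction must be classified as very severe".

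None of these gives a rule for the repeated renal band or for 1.5 to <2 ×. The SAP supplies none either.

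**The concern.** A severity scale should not move down when one of its own components gets worse and everything else stays the same. Here a ratio of 1.3 counts toward two grades and a ratio of 1.7 counts toward none. Because a grade needs only two criteria, the renal item can decide it.

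VOD is a named part of the secondary safety endpoint. In Study B1931022 it followed HSCT in 18 of 79 inotuzumab-treated patients, and five of those cases were fatal (Protocol 2.2.2.1.3.1 and 2.2.2.1.3.2). The line between Grade 2 and Grade 3 separates moderate from severe disease, and Protocol Appendix 10 describes Phase 3 outcomes in Grade 3 or 4 cases. With few cases expected, one misgraded case would be visible in any description of severity.

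**Working it through.** **Inputs.** Table 9 and its footnotes only. No sample size, power or alpha figure is involved, and the plan states no figure to reproduce.

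**Worked example.** Bilirubin 2.5 mg/dL without doubling in 48 h (Mild), symptoms >7 days (Mild), transaminases ≤2 × ULN (Mild), weight +6% (Moderate or Severe under footnote a), no multi-organ dysfunction, fewer than two risk factors.

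- Ratio 1.3, as printed: renal is a Severe criterion. With that criterion present, weight also counts as Severe. Two Severe criteria give **Grade 3**.
- Ratio 1.7, as printed: renal meets no criterion. Weight reverts to Moderate and stands alone. Three Mild criteria remain, giving **Grade 1**.
- If footnote b applies, the results are Grade 3 and Grade 2.
- The Any time entry in the Very severe column does not change these results. If counted, it is one Grade 4 criterion and two are needed.
- With a Severe band of ≥1.5 and <2 ×: at 1.3, renal and weight are both Moderate, so Grade 2. At 1.7, both are Severe, so Grade 3.

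**All combinations.** Time (3 levels) × bilirubin (4) × doubling (2) × transaminases (4) × weight (3) = 288 profiles, none with multi-organ dysfunction. Each was graded at 1.3 × and at 1.7 × with everything else fixed. The table counts profiles whose grade is lower at 1.7 × than at 1.3 ×.

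| Reading | As printed | Severe band ≥1.5 and <2 × |
|---|---|---|
| No footnote b, Any time not counted | 82 | 10 |
| No footnote b, Any time counted | 31 | 3 |
| Footnote b for all, Any time not counted | 53 | 10 |
| Footnote b for all, Any time counted | 17 | 3 |

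The 82 are 33 falls from Grade 3 to 1, 29 from 3 to 2, 10 from 3 to no grade, and 10 from 2 to 1. The 10 (or 3) falls left after the correction come from the two-criteria rule. For example, with Moderate transaminases, Mild time and bilirubin, and weight gain <5%, a ratio of 1.3 gives two Moderate criteria (Grade 2). A ratio of 1.7 leaves one Moderate and one Severe criterion, so the two Mild ones decide (Grade 1).

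The profiles are unweighted combinations, not patients. They show that the reversal occurs under every reading tested. They do not show how often it would occur.

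**Where the grade goes.**

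- Diagnosis in section 8.4.8.2 has no renal item.
- All VOD is an SAE whatever its severity, and dosing stops for any possible, probable or confirmed case (8.4.8.2, 7.1.1.1).
- The VOD analyses in Protocol 9.4.2 and SAP 6.6.1.1 are counts, percentages and risk-factor splits, with no split by grade. SAP Appendix 2 takes the veno-occlusive terms at any grade.
- AE intensity follows CTCAE v5.0 (Protocol 10.3.3). The SAP takes the grade from the CRF: "Seriousness, toxicity grade, action taken (interruption, reduction, and withdraw) are as reported by the investigator on the adverse event CRF".

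**The case against.** **A conversion fault.** The text was read from PDF and tables can break. A merged cell read twice would explain the repeated band but not the missing interval. A converter that repeated the neighbouring cell would explain both. The four cells are complete and in order, but this cannot be excluded. It makes checking the source table the first step of any correction.

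**A deliberate overlap, as for weight.** Footnote a explains the shared weight band and names weight only. A deliberate overlap would still leave 1.5 to <2 × unassigned.

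**Almost no reach into the analysis.** This largely stands. Every renal cell is relative to the value at HSCT, so the row works only after transplant. The SAP's on-treatment period ends the day before new anti-cancer therapy (SAP 3.5, 5.2.5), and the protocol treats transplant conditioning as such therapy (Table 1 footnote 19; Table 2 footnote 5). If conditioning is recorded on the follow-up therapy pages, which the documents do not say outright, these cases fall outside the summary tables. The post-HSCT SAE tables in SAP 6.6.1 are by term, not by grade. A reader might infer that the Grade 3-5 AE tables or the VOD rates are distorted, but the documents show no planned table that uses a Table 9 grade.

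**Grades too high at 1.3 ×.** A reader might also infer that 1.3 × is over-graded. That depends on which repair is assumed. If the shared band were instead extended to ≥1.2 and <2 ×, no profile would be too high at 1.3 ×. Only the gap, and the fall in grade within it, stand without choosing a repair.

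**Conclusion.** The point holds as a minor error, wrong as written. As printed, Table 9 assigns one renal band to two grades and assigns 1.5 to <2 × to none. Without multi-organ dysfunction, a post-transplant VOD case can therefore drop in grade as kidney function worsens, by up to two grades in the example.

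The consequence is limited to the recorded VOD severity grade and to any description of post-transplant VOD severity that draws on it.

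No number of affected patients can be given. Multiplying an expected case count by the profile shares would treat unweighted combinations as frequencies, and it would assume that every case has a ratio between 1.2 and 2. The lower end is zero.

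The conclusion assumes that the printed cells are faithful to the protocol's table. The replacement band is the only unassigned interval, but the documents do not state it.

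**What to change.** Check the Severe renal cell against the source table and against the classification cited in section 8.4.8.2 (reference 20). If the check confirms it, set the cell to ≥1.5 and <2 × baseline at HSCT by protocol clarification letter. Re-derive any VOD grade already assigned using the renal row. If the classification intends a shared band, state that band up to <2 × with a footnote like the one for weight.

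The corrected band removes most but not all falls in grade. The 10 of 288 that remain (3 if Any time counts) belong to the two-criteria rule and need no change here.

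The cost is one table cell and a re-check of a few cases. Assuming Study B1931022 rates, 44 × 18/164 = 4.8 post-HSCT VOD cases would be expected. No new procedures or data are needed.

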#### 8.4.9. Medical Device Deficiencies

Not applicable.

#### 8.4.10. Medication Errors

Medication errors may result from the administration or consumption of the study intervention by the wrong participant, or at the wrong time, or at the wrong dosage strength.

Medication errors are recorded and reported as follows:

Recorded on the Medication Error Page of the CRF	Recorded on the Adverse Event Page of the CRF	Reported on the CT SAE Report Form to Pfizer Safety Within 24 Hours of Awareness
All (regardless of whether associated with an AE)	Any AE or SAE associated with the medication error	Only if associated with an SAE

Medication errors include:

- Medication errors involving participant exposure to the study intervention;
- Potential medication errors or uses outside of what is foreseen in the protocol that do or do not involve the study participant.

Such medication errors occurring to a study participant are to be captured on the medication error page of the CRF, which is a specific version of the AE page.

Whether or not the medication error is accompanied by an AE, as determined by the investigator, the medication error is recorded on the medication error page of the CRF and, if applicable, any associated AE(s), serious and nonserious, are recorded on an AE page of the CRF.

In the event of a medication dosing error, the sponsor should be notified within 24 hours.

Medication errors should be reported to Pfizer Safety within 24 hours on a CT SAE Report Form **only when associated with an SAE**.

### 8.5. Pharmacokinetics

Blood samples of approximately 4 mL, to provide a minimum of 1.35 mL of serum, will be collected for measurement of serum concentrations of inotuzumab ozogamicin and free calicheamicin as specified in the [SoA \(Table 1\)](#). Instructions for the collection and handling of biological samples will be provided in the laboratory manual or by the sponsor. The actual date and time (24-hour clock time) of each sample will be recorded.

The actual times may change, but the number of samples will remain the same. All efforts will be made to obtain the samples at the exact nominal time relative to dosing. Collection of samples up to and including 10 hours after dose administration that are obtained within 10% of the nominal time (eg, within 6 minutes of a 60-minute sample) relative to dosing will not be captured as a protocol deviation, as long as the exact time of the collection is noted on the source document and data collection tool (eg, CRF). Collection of samples more than 10 hours after dose administration that are obtained  $\leq$ 1 hour away from the nominal time relative to dosing will not be captured as a protocol deviation, as long as the exact time of the collection is noted on the source document and data collection tool (eg, CRF).

PFIZER CONFIDENTIAL

CT02-GSOP Oncology Clinical Protocol Template (01 April 2022)

Page 72

Samples will be used to evaluate the PK of inotuzumab ozogamicin and free calicheamicin. Each serum sample will be divided into three aliquots (1 for inotuzumab ozogamicin and 2 for free calicheamicin). Samples collected for analyses of inotuzumab ozogamicin and free calicheamicin concentration may also be used to evaluate safety or efficacy aspects related to concerns arising during or after the study, for metabolite identification and/or evaluation of the bioanalytical method, or for other internal exploratory purposes.

Genetic analyses will not be performed on these serum samples. Participant confidentiality will be maintained.

Samples collected for measurement of serum concentrations of inotuzumab ozogamicin and free calicheamicin will be analyzed using a validated analytical method in compliance with applicable standard operating procedures (SOPs).

The PK samples must be processed and shipped as indicated in the instructions provided to the investigator site to maintain sample integrity. Any deviations from the PK sample handling procedure (eg, sample collection and processing steps, interim storage or shipping conditions), including any actions taken, must be documented and reported to the sponsor. On a case by case basis, the sponsor may make a determination as to whether sample integrity has been compromised.

